11.5.4 Concomitant Medications or Treatments

The number and percentage of patients taking prior and concomitant medications will be summarized by therapeutic class and preferred term using descriptive statistics. All data will be recorded as follows:

- Prior medication: ended before first day of study drug.
- Concomitant medication: ongoing at first day of study drug or started after first day of study drug.

11.5.5 Efficacy Analysis

All efficacy analyses will be performed using the FAS.

11.5.5.1 Part A

The primary endpoint for Part A is the overall response rate (ORR) within a group. It will be defined as the percentage of patients achieving a BOR of confirmed CR and/or PR as assessed by the investigator. The ORR will be presented with its 95% confidence intervals (CIs).

All response assessments will be presented using swimmer plots and will be listed by patient.

Sensitivity analyses of the primary analysis will include similar analyses using PP analysis set.

Analyses of secondary efficacy endpoints will include Kaplan-Meier estimates and curves, median DoR and respective 95% CIs for analysis of:

- Duration of response (DoR): time from first response to disease progression or death. Patients with no event will be censored at the last available tumor assessment. This analysis will be based on investigator assessment.
- Progression-free survival over 18 months (PFS): time from first day of trial medication to disease progression or death. Patients with no event will be censored at the last available tumor assessment. This analysis will be based on investigator assessment.
- Overall survival over 18 months (OS): time from first day of trial medication to death. Patients with no event will be censored at the last date the patient is known to be alive.

11.5.5.2 Part B

The primary endpoint for Part B is the Progression-Free Survival over 18 months (PFS), defined as time from first day of trial medication to disease progression as adjudicated by the independent review committee or death. Patients with no event will be censored at the last available tumor assessment. PFS will be analyzed using Kaplan-Meier estimates and curves, median PFS and respective 95% CIs.

For each histology, PFS curves will be compared between ulixertinib and physician's choice of treatment using Log Rank Test. The hazard ratio including 95% CI will be calculated by Cox's Proportional Hazards model.

Sensitivity analyses of the primary analysis will include similar analyses based on investigator response assessment and using PP analysis set.

Analyses of secondary efficacy endpoints will include analyses similar to PFS analysis for:

- Overall survival over 18 months (OS): time from first day of trial medication to death. Patients with no event will be censored at the last date the patient is known to be alive.
- Duration of response (DoR): time from first response to disease progression or death. Patients with no event will be censored at the last available tumor assessment. This analysis will be based on assessment as adjudicated by the independent review committee and replicated on investigator assessment.
- Overall response rate (ORR), defined as the percentage of patients achieving a BOR of confirmed CR and/or PR, will be presented with its 95% CIs and compared between ulixertinib and physician's choice of treatment using a Chi-square test. This analysis will be based on assessment as adjudicated by the independent review committee and replicated on investigator assessment.

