7 STUDY POPULATION

7.1 INCLUSION CRITERIA

Patients must meet all of the inclusion criteria to be eligible:

1. Patients with a locally advanced or metastatic malignancy, that has progressed following systemic therapy for their disease, if available, or for which the patient is not a candidate or refuses.
2. Tumor harboring a MEK or atypical BRAF alteration.
3. Provided signed and dated informed consent prior to initiation of any study-related procedures that are not considered standard of care (SoC).
4. Male or female patients aged ≥ 18 years.
5. Patients must have measurable disease by RECIST version 1.1.
6. Eastern Cooperative Oncology Group (ECOG) performance status of 0 - 2.
7. Adequate renal function (using Cockcroft-Gault) [creatinine ≤ 1.5 times ULN (upper limit of normal)] or a glomerular filtration rate (GFR) of ≥ 50 mL/min.
8. Adequate hepatic function [total bilirubin ≤ 1.5 times ULN; AST (aspartate transaminase) and ALT (alanine transaminase) ≤ 3 times ULN or ≤ 5 times ULN if due to liver involvement by tumor].
9. Adequate bone marrow function (hemoglobin ≥ 9.0 g/dL; platelets $\geq 100 \times 10^9$ cells/L; absolute neutrophil count $\geq 1.5 \times 10^9$ cells/L).
10. Adequate cardiac function:
 - Left ventricular ejection fraction (LVEF) of $>50\%$ as assessed by multi-gated acquisition (MUGA) or ultrasound/echocardiography (ECHO); and
 - A corrected QT interval (QTc) <480 ms by the Fridericia method (QTcF).
11. Contraception:
 - a. For women: Negative pregnancy test for females of child-bearing potential; must be surgically sterile, postmenopausal (no menstrual cycle for at least 12 consecutive months), or compliant with a medically approved contraceptive regimen during and for 3 months after the treatment period. Abstinence is not considered an adequate contraceptive regimen.
 - b. For men: Must be surgically sterile, or compliant with a medically approved contraceptive regimen during and for 3 months after the treatment period.

12. Willing and able to participate in the trial and comply with all trial requirements.
13. Patients with a prior or concurrent malignancy whose natural history or treatment does not have the potential to interfere with the safety or efficacy assessment of the investigational agent may be included after consultation with the medical monitor.

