10.1.4 Vital Signs and Physical Examination

Height should be recorded at screening only. Body weight should be recorded at each visit.

Vital sign records should include body temperature, systolic/diastolic blood pressure (BP), and pulse rate. BP should be assessed on the same arm during the study.

Full physical examination evaluations at screening should include general appearance, skin, neck, eyes, ears, nose, throat, lungs, heart, abdomen, back, lymph nodes, extremities, and neurological examinations. Subsequent targeted physical exams should include body systems as appropriate.

Performance status (ECOG) should be assessed within 72 hours before start of study treatment and at each study visit (see Appendix 3).

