11.2.2 Part B

It is not possible to accurately calculate the required sample size until the histologies of interest have been confirmed. Once the histologies of interest have been confirmed these calculations will be repeated and the final sample size confirmed.

Approximately 80-100 patients will be randomized, using a 2:1 ratio, for each histology group in Part B.

Using a 2-sided, log-rank test with a 5% alpha, and assuming a median PFS of 1.7 to 8.5 months (depending on histology) in the physician's choice arm and twice as long on the ulixertinib arm, approximately 80 to 100 patients will be required in each group to achieve 80% power to show a statistically significant difference between the arms. This also assumes that each group will take approximately 24 months to accrue and the analysis is expected to be performed 18 months following the last patient accrued. The anticipated loss to follow-up is estimated to be 10%.

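### The Part B primary PFS comparison (and OS) uses no baseline covariate, although ECOG 0–2 is known before randomisation; adjusting for it costs little and gains power if ECOG is prognostic

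*Protocol*

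**What the plan says.** Protocol 11.5.5.2 makes PFS the Part B primary endpoint. Each histology is tested separately by log-rank, and "The hazard ratio including 95% CI will be calculated by Cox" regression. No covariate or stratum is named, and OS follows the PFS method. SAP 9.8.3 and 9.8.4 repeat the log-rank test, allow another test if hazards are not proportional, and name no stratum either.

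The design does not balance ECOG. Protocol 8.3 and 11.3 and SAP 6.3 describe 2:1 allocation through the IxRS without any stratification factor.

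ECOG is available. Protocol 7.1 admits patients with "Eastern Cooperative Oncology Group (ECOG) performance status of 0 - 2", and 8.3 requires eligibility to be confirmed before the randomisation call. Protocol 10.1.4 adds that "Performance status (ECOG) should be assessed within 72 hours before start of study treatment". The SAP uses ECOG only descriptively (9.3 and 9.9.3.6).

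On size, Protocol 11.2.2 states "Approximately 80-100 patients will be randomized, using a 2:1 ratio, for each histology group in Part B".

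**The concern.** In a time-to-event comparison, leaving out a strong prognostic factor moves the unadjusted hazard ratio closer to 1 than the ratio within levels of that factor, and the test loses power. Each histology would have only about 27 to 33 control patients, so ECOG could also differ between arms by chance. The sample size has almost no margin above 80% power. If ECOG predicts PFS strongly and the assumed effect holds within ECOG levels, the unadjusted test would fall short of its target, and a variable already on the case report form would recover most of the shortfall.

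**Working it through.** **1. The plan's own figure.** Inputs from Protocol 11.2.2: "Using a 2-sided, log-rank test with a 5% alpha"; control median 1.7 to 8.5 months; median "twice as long on the ulixertinib arm", so HR 0.5 under exponential PFS; 80% power; 2:1 allocation; 24 months' accrual plus 18 months; 10% loss.

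Events (Schoenfeld) = (1.960 + 0.842)² / [(2/3)(1/3)(ln 0.5)²] = 7.849 / (0.2222 × 0.4805) = 73.5, so 74.

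- Without loss, the event probability averaged over arms and entry times is 0.997 at median 1.7 and 0.762 at median 8.5. Then 74/0.997 gives 75 patients and 74/0.762 gives 98.
- With loss as exponential censoring (10% over 42 months), the probabilities are 0.987 and 0.742, giving 76 and 100 patients. Power is 82.7% at N = 80, median 1.7, and 80.3% at N = 100, median 8.5.

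The stated 80 to 100 patients is reproduced.

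**2. Chance imbalance.** Assume 65% of patients have ECOG 1–2. The standard error of the difference in that proportion between arms is √[0.65 × 0.35 × (1/27 + 1/53)] = 0.113 at N = 80, and √[0.65 × 0.35 × (1/33 + 1/67)] = 0.101 at N = 100. A difference above 10 percentage points then occurs in about 38% and 32% of trials.

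**3. Effect of adjusting.** The documents give neither the ECOG distribution nor its effect on PFS, so both are assumed. The setup is 10,000 trials per setting, treatment HR 0.5 within each ECOG level, and 10% random loss. Monte Carlo error is about √(0.8 × 0.2/10,000) = 0.4 points. Power in %:

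| Setting (ECOG 0/1/2 mix) | HR per level | Log-rank | Log-rank, three ECOG strata | Cox with ECOG | Cox minus log-rank |
|---|---|---|---|---|---|
| N=80, median 1.7 (35/55/10) | 1.0 | 81.7 | 78.3 | 80.6 | −1.1 |
| | 1.25 | 80.9 | 79.1 | 81.2 | +0.3 |
| | 1.5 | 78.4 | 78.6 | 81.0 | +2.6 |
| | 2.0 | 72.4 | 78.5 | 80.6 | +8.2 |
| N=100, median 8.5 (35/55/10) | 1.0 | 82.3 | 80.3 | 81.5 | −0.8 |
| | 1.25 | 82.0 | 80.3 | 82.0 | 0.0 |
| | 1.5 | 79.5 | 79.7 | 81.1 | +1.6 |
| | 2.0 | 73.3 | 78.5 | 80.0 | +6.7 |
| N=80, median 1.7 (30/40/30) | 1.0 | 82.7 | 78.9 | 82.1 | −0.6 |
| | 1.25 | 80.4 | 78.4 | 81.4 | +1.0 |
| | 1.5 | 76.5 | 78.5 | 81.4 | +4.9 |
| | 2.0 | 67.7 | 77.7 | 80.1 | +12.4 |
| N=100, median 8.5 (30/40/30) | 1.0 | 82.2 | 79.8 | 81.6 | −0.6 |
| | 1.25 | 80.9 | 79.9 | 81.1 | +0.2 |
| | 1.5 | 77.6 | 80.0 | 81.6 | +4.0 |
| | 2.0 | 68.6 | 78.1 | 79.2 | +10.6 |

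Adding the crossed settings (N = 80 with median 8.5, N = 100 with median 1.7), the adjusted Cox model changes power by −0.4 to −1.1 points at HR 1.0, 0 to +1.0 at 1.25, +1.6 to +4.9 at 1.5, and +6.7 to +12.7 at 2.0.

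**4. Two strata instead of three.** Stratifying on all three levels loses 1.9 to 3.8 points when ECOG has no effect. Stratifying by 0 against 1–2 loses 0.6 to 2.0. With an assumed 35/50/15 mix (5,000 trials per setting), unstratified against two-strata power is:

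- N = 80, median 1.7: 82/80, 80/79, 77/78 and 70/77% at HR 1.0, 1.25, 1.5 and 2.0 per level.
- N = 100, median 8.5: 83/82, 81/81, 79/80 and 73/77%.

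**5. Type I error** (N = 80, HR 1.5 per level): 5.6% for the log-rank test, 5.2% for the stratified log-rank and 5.4% for the adjusted Cox model. The three are similar.

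**The case against.** The case for leaving the plan alone is substantial.

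- **Validity.** An unstratified log-rank test is a legitimate primary test in a randomised trial. A reader might infer that it is biased or invalid. It is not: type I error is about the same for all methods, and the smaller unadjusted hazard-ratio effect is a different (marginal) quantity, not an error.
- **Size.** A reader might infer that power is being given up for nothing. The documents do not support that. They contain no ECOG effect on PFS, and the histologies are not chosen. At 1.25 per level the gain is nil to 1 point with the Cox model and nil or slightly negative with two strata. A large gain needs a doubling per level, so that ECOG 2 carries four times the hazard of ECOG 0.
- **The stated power.** A reader might also infer that 80% is wrong. Protocol 11.2.2 doubles the arm medians and does not say whether the effect holds within ECOG levels. The simulation assumes that it does. If the overall medians double, the stated power may well stand, and adjustment would add to it.
- **Choice of factor.** Alteration type or prior lines of therapy could be argued for instead of ECOG.
- **Timing.** Part B patients are randomised before Visit 2, and Protocol 10.3.1.2 lets the 72-hour ECOG assessment be done at Visit 2. That value could come after allocation.
- **Status.** SAP sections 4 and 7.2 defer the Part B detail to a later version, and 7.2 records that the study stopped during Part A.

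All of these stand as limits on size, wording and urgency. None removes the point: the variable is already needed for eligibility, the possible loss is small and bounded, and the deferred SAP version is where the choice belongs.

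**Conclusion.** The point holds as a recommended improvement, not as an error. The Part B PFS and OS comparisons use no covariate, and ECOG 0–2 is known before randomisation but not balanced by design.

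If ECOG is not prognostic, adjustment costs about 1 point with a Cox covariate and at most about 2 with two strata. If it is, the adjusted Cox model gains about 2 to 5 points at a hazard ratio of 1.5 per level and about 7 to 13 at 2.0. The two-strata test gains less: about 1 point at 1.5, and 4 to 7 at 2.0.

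These figures rest on exponential PFS, HR 0.5 within ECOG level, and assumed ECOG mixes and effects. Practical weight is low because Part B did not proceed under the current SAP. The point applies if the Part B plan is taken up.

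**What to change.** In Protocol 11.5.5.2 and the updated Part B SAP (9.8.3 and 9.8.4), choose one of two primary analyses before Part B opens:

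- *The primary PFS comparison and hazard ratio come from a Cox model with treatment and ECOG status (0, 1, 2) as covariates; or*
- *The primary PFS comparison is a log-rank test, with a Cox model for the hazard ratio, both stratified by ECOG 0 against 1–2.*

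In either case add: *ECOG is the last value recorded before randomisation. The hazard ratio is conditional on ECOG. The unstratified log-rank test and unadjusted hazard ratio are supportive. OS is analysed in the same way.*

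Three details matter:

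- Changing only the hazard-ratio model would leave the power of the log-rank test unchanged, so the test must change too. Protocol 11.2.2 and SAP 6.4 should then name the same test.
- The SAP's general baseline rule (7.8, last value before first dose) should not be used here, because it could pick up a Visit 2 value taken after open-label allocation. The value used to confirm eligibility serves.
- Three separate strata should be avoided at this size.

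The cost is a few sentences and one model term, with no new data collection, at most about 2 points of power if ECOG does not matter, and a conditional rather than marginal hazard ratio. Any Part A data on ECOG and PFS could inform the choice.

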11.5.6 Pharmacokinetic (PK) / Pharmacodynamic (PD) Data

Pharmacokinetic parameters of ulixertinib (BVD-523) and selected metabolites will be measured on Visit 4 (Day 15) in Part A only, this will be a single time-point collection prior to taking study drug on this day (trough at steady state).

Pharmacokinetic values will be presented in by-patient listings, sorted by site, patient identifier, and dose.

In Part A only, the effects of ulixertinib on pharmacodynamic markers will be evaluated. Collections will include ctDNA, tissue biopsies and/or blood to assess biomarkers. Assays include, but are not limited to, phosphorylation of RSK from whole blood, Reverse Phase Protein Arrays (RPPA) to assess protein levels, e.g. DUSP 4/6, plus Nanostring and/or RNA-exome to assess mRNA expression in tissue pre- and post-ulixertinib treatment. Biomarkers will be explored and listed as appropriate.

11.5.7 Safety Analysis

All safety summaries will be provided for the safety analysis set.

11.5.7.1 Adverse Events (AE)

AEs will be coded using the Medical Dictionary for Regulatory Activities (MedDRA). System Organ Class, High-Level Group Term, High Level Term, Preferred Term, and Lower-Level Term will be attached to the clinical database.

AEs will be summarized based on the date of onset for the event. Summaries (number and percentage of patients) of treatment-emergent AEs will be provided by System Organ Class and Preferred Term, by group/tumor histology and overall.

Treatment-emergent adverse event (TEAE) is defined as any AE that emerges during treatment having been absent pre-treatment or worsens relative to the pre-treatment state.

Events that are considered study drug-related, deaths, SAEs, and AEs resulting in study drug discontinuation will also be tabulated by System Organ Class and Preferred Term.

A tabulation will also be provided that summarizes treatment-emergent AEs by maximum severity (i.e., CTCAE grade).

All AEs, including treatment-emergent and non-treatment-emergent AEs, will be listed in patient data listings.

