**Table 2. Analysis periods**

Phase	Period	Definition
Part A and Part B	PRE-TREATMENT	From informed consent form (ICF) signature to the day before first dose of study treatment.
	ON-TREATMENT	From the day of first dose of study treatment to ≤14 ± 3 days after last dose of study treatment (date of EOT visit), or the earliest date of subsequent anti-cancer drug therapy – 1 day, whichever occurs first.
	FOLLOW-UP	From day ≤14 ± 3 after last dose of study treatment, or the earliest date of subsequent anti-cancer drug therapy, whichever occurs first, to end of study. End of study is date of completion / discontinuation from the study as collected in the CRF or the last recorded assessment in the database if the patient has not completed/discontinued the study at the time of the analysis.

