### **Categorical data**

Categorical data will be summarized using n and percentage.

- All categories will be presented, even if no patients are counted in a particular category, unless otherwise stated.
- A Missing category will be displayed in all tables for categories where at least one missing value exists, unless otherwise specified.
- Counts of zero in any category will be presented without percentage.
- All summary percentages will be calculated using N, unless otherwise stated in a footnote.
- For AEs, medical history, prior and concomitant medications, the counts are based on single counts of patients with multiple events/treatments under the same category, while the percentages are calculated using N. Counts will be displayed by descending order of frequency for the overall group by dictionary hierarchy.

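### Part B adverse-event tables use no time at risk, so if ulixertinib is taken for longer, as the sizing implies, events that accrue over time would look more frequent on it at an equal monthly rate

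*Protocol*

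**What the plan says.** Protocol 11.5.7.1 states that "Summaries (number and percentage of patients) of treatment-emergent AEs will be provided by System Organ Class and Preferred Term". SAP 9.9.1 does the same for all, related, serious and grade 3 or higher events. SAP 7.8 (Categorical data) counts each patient once per category, "while the percentages are calculated using N". For Part B, SAP 7.8 (Summary presentation) and the general programming notes of the table shells give ulixertinib histology columns, one comparator column that pools every physician's-choice regimen, and an overall column.

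A treatment-emergent event is one arising in the on-treatment period, which SAP Table 2 defines as "From the day of first dose of study treatment to" about 14 days after the last dose, or the day before another anti-cancer drug begins if that is sooner. The protocol synopsis (Patient Duration) and SAP 6.1 continue therapy until progression, intolerable toxicity, study closure or another stopping criterion. Protocol 11.2.2 sizes Part B by "assuming a median PFS of 1.7 to 8.5 months (depending on histology) in the physician's choice arm and twice as long on the ulixertinib arm".

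Only two other kinds of adverse-event summary are planned. The maximum-grade tables add raw event counts. There are also splits at the end of Cycle 1, but only for events leading to discontinuation, interruption or dose reduction. Neither uses patient-time.

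**The concern.** The window in which an event can be counted lengthens with treatment. If ulixertinib delays progression as the sizing assumes, its patients are watched for longer, and the share with at least one event rises even when the monthly rate is the same in both arms. Someone reading the ulixertinib and comparator columns side by side could not tell extra toxicity from extra observation, and the confusion would grow with efficacy.

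**Working it through.** **Plan's own figure.** The test is described as "Using a 2-sided, log-rank test with a 5% alpha", with 2:1 allocation and 80% power. A doubled median under exponential PFS is a hazard ratio of 0.5. Schoenfeld events = (1.960 + 0.842)² / [(2/3)(1/3)(ln 0.5)²] = 73.5, so 74. With 24 months of accrual, 18 months of follow-up and 10% exponential loss over 42 months, the overall event probability is 0.987 at a control median of 1.7 months and 0.742 at 8.5 months. That gives N = 76 and 100 (75 and 98 with no loss), so the stated 80 to 100 is reproduced. The doubling of PFS is therefore what the sizing rests on.

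**Inputs.** Control medians of 1.7 and 8.5 months, the doubling and the calendar come from Protocol 11.2.2. The 14-day tail (w = 14/30.4375 = 0.46 months) comes from SAP Table 2. The documents give no monthly adverse-event rate, so I assume a constant hazard λ, equal in both arms, from 0.02 to 0.20 per month. I also assume that time on treatment follows PFS and that the same tail applies to the comparator.

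**Formula.** With stopping hazard μ = ln 2 / median, P(event) = 1 − exp(−λw) · μ/(μ + λ).

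**Worked example.** Control median 1.7 months, λ = 0.10: μ is 0.4077 on control and 0.2039 on ulixertinib, and exp(−0.046) = 0.955.
- Control: 1 − 0.955 × 0.4077/0.5077 = 23.3%.
- Ulixertinib: 1 − 0.955 × 0.2039/0.3039 = 35.9%.

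The gap is 12.6 points with no true difference in rate.

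**With the plan's calendar.** Exposure is capped at a time C, uniform on 18 to 42 months, so the factor μ/(μ + λ) becomes the average over C of μ/(μ + λ) · (1 − exp(−(μ + λ)C)) + exp(−(μ + λ)C). Excess on ulixertinib, in percentage points:

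| λ per month | Control median 1.7 | Control median 8.5 |
|---|---|---|
| 0.02 | 4.2 | 8.5 |
| 0.05 | 8.5 | 13.5 |
| 0.10 | 12.6 | 14.2 |
| 0.20 | 15.2 | 10.9 |

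At 8.5 months and λ = 0.05 the percentages are 38.4% v 51.8% (13.5 points before rounding). The cap matters there: mean exposure is 12.3 v 24.5 months uncapped but 11.0 v 17.0 capped, a ratio of 1.54, and without it the gap would be 16.7 points. At 1.7 months the means are 2.45 v 4.91 and the cap changes almost nothing.

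**What shrinks the excess.**
- *Stopping for reasons other than progression*, assumed at 0.05 or 0.10 per month in both arms and added to μ. The 1.7-month example (λ = 0.10) falls from 12.6 to 9.9 or 7.9 points. The 8.5-month example (λ = 0.05) falls to 7.8 or 4.5 points uncapped, and 7.2 or 4.4 with the calendar cap.
- *Events confined to the first 28 days* (T = 28/30.4375 months, no tail): P = λ/(λ + μ) · (1 − exp(−(λ + μ)T)). With λ of 0.2 and 0.5, the excess runs from 0.3 points (16.2% v 16.5%, median 8.5) to 2.7 points (31.2% v 33.9%, median 1.7).

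**Does the remedy work?** In a simulation of one million patients per arm, without tail or cap, patients with a first event per patient-month at risk recovered the equal rate. Crude 19.7% v 32.9% became 0.100 v 0.100 per month (median 1.7, true rate 0.10). Crude 38.0% v 55.0% became 0.050 v 0.050 (median 8.5, true rate 0.05).

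**The case against.** A reader might infer that the Part B safety objective is answered with a bias against ulixertinib. The documents do not support that. Protocol 5.2.2 sets the safety objective for ulixertinib alone, whereas the neighbouring survival and response objectives add the comparison with physician's choice, and SAP 9.9 limits safety to descriptive statistics. Protocol 11.5.7.1 tabulates by group or histology and names no arm. The contrast arises only because the SAP's Part B columns put the comparator alongside. That comparator is pooled across histologies, so the within-histology contrast modelled here is not exactly what the shells would print.

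Nor is the direction fixed. SAP 7.1 defines study treatment as ulixertinib, and Table 2 ties the window to study treatment, so the comparator's window is not defined. Control patients may cross over at progression (Protocol 6.1.2 and 8.3), and nothing says which column their later events enter. If they enter the comparator column, the excess would shrink and could reverse.

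The doubling is also an assumption about PFS, not time on treatment. Protocol 8.1.3 and 9.2 give other reasons to stop. The raw event counts, the Cycle 1 splits and the onset days in the event listing give partial information, so it would be wrong to say that only crude percentages are planned.

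Finally, SAP 4 and 7.2 defer Part B detail to a later version, and 7.2 records early termination during Part A. SAP 9.6 expressly postpones Part B exposure. However, 9.9 applies its safety summaries to both parts with no such deferral for adverse events.

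These points limit the size and the practical consequence. They do not supply a table that uses time at risk.

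**Conclusion.** The point holds as a cheap improvement, not as a defect in a planned comparison. As written, the Part B tables cannot separate a higher event rate from longer observation for events that accrue over time.

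Under equal constant hazards of 0.02 to 0.20 per month, time on treatment following PFS and the plan's calendar, the apparent excess on ulixertinib is 4.2 to 15.2 points at a control median of 1.7 months and 8.5 to 14.2 points at 8.5 months. With assumed other-cause stopping of 0.05 to 0.10 per month, the two worked examples drop to about 8 to 10 and about 4 to 8 points. Early-onset events are barely affected. The hazards and stopping rates are mine, not the documents', and the direction presumes that the comparator window ends at crossover. Since the study stopped during Part A, the consequence is confined to any later use of this plan.

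**What to change.** In the Part B update of SAP 9.9.1:

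- Keep the crude tables.
- Define the comparator on-treatment window from first to last dose of physician's choice, with the same post-dose allowance as ulixertinib, and end it at crossover. Show post-crossover events separately.
- For all, related, grade 3 or higher and serious treatment-emergent events, add by histology and arm (1) patients with a first event divided by patient-months at risk, counted to first event or end of window, and (2) the percentage of patients with an event in Days 1-56.
- Base any between-arm safety statement on these two measures.

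The cost is a few extra tables from dates already collected. Sizing and clinical procedures are unchanged. The exposure-adjusted rate assumes a roughly constant hazard, and the common-window percentage is there to offset that weakness.
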